The overall prevalence of IBS in the pediatric population is low. IBS prevalence in children across the United States, based on parental reports, ranges from 1.2% to 2.9%, while school-based studies in Colombia and Sri Lanka found a prevalence of IBS of 4.9% and 5.4%, respectively ([Hyams 2016](#)). In adults, although not life-threatening, because of its chronic relapsing course, IBS is associated with impaired quality of life and high direct and indirect medical costs such as absenteeism from work ([Thompson 1999](#)). In children and adolescents, IBS has been associated with significant impairment as increased rates of school absenteeism, health-care utilization and family disruption are common ([Chiou and Nurko 2010](#)).

The primary objective of LIN-MD-66 is to assess the long-term safety of linaclotide administered to participants with FC (total exposure with linaclotide for 24 weeks) or IBS-C (total exposure with linaclotide for 52 weeks) who have completed study intervention in Study LIN-MD-62, LIN-MD-63, or LIN-MD-64.

Objectives and Assessments:

Objectives	Assessments
Primary The objective of this study is to assess the long-term safety of linaclotide in pediatric participants with FC (total exposure with linaclotide for 24 weeks) or IBS-C (total exposure with linaclotide for 52 weeks) who have completed study intervention in Study LIN-MD-62, LIN-MD-63, or LIN-MD-64.	The safety assessments will include monitoring of adverse events (AEs), clinical laboratory assessments (clinical chemistry, complete blood count [CBC], urinalysis), vital sign measurements (including postural vital signs), electrocardiograms (ECGs), physical examinations, height, and weight.

Overall Study Design:

LIN-MD-66 is a long-term safety study with 24 weeks (FC participants) or 52 weeks (IBS-C participants) of linaclotide exposure that will enroll pediatric participants (6-17 years of age) with FC or IBS-C who completed study intervention in Phase 2 study LIN-MD-62 or LIN-MD-63, or Phase 3 study LIN-MD-64, based on the individual study criteria. For FC participants enrolling from studies LIN-MD-62 and LIN-MD-64, and IBS-C participants enrolling from study LIN-MD-63, linaclotide treatment will be open-label. For IBS-C

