- ^d Fecal impaction is defined as a hard mass in the lower abdomen identified on physical examination or a dilated rectum filled with a large amount of stool on rectal examination. If fecal impaction is documented during an optional repeat physical examination, the sponsor must be notified. If a rectal examination is performed, the medically qualified site personnel should assess for and document the presence of anal wink and normal anal tone.
- ^e A fecal impaction assessment is performed at the study Day 1 Visit (Visit 2) prior to study intervention administration. If the participant is impacted at Visit 2, the participant would not be eligible for the study.
- ^f Vital signs include weight, temperature (oral, rectal, or tympanic), and respiratory rate. Postural vital signs (supine and standing) include pulse rate and systolic and diastolic blood pressure. At all visits, postural vital signs must be obtained after participants have been in a supine position for at least 2 to 3 minutes, followed by a standing position for at least 1 minute.
- ^g Clinical laboratory tests consist of clinical chemistry, hematology, and urinalysis. All laboratory tests requiring blood draws should be collected at the same time.
- ^h The urine drug screen will be obtained at Screening (Visit 1) for all participants 12 to 17 years of age and, only if deemed necessary by the investigator, for participants 6 to 11 years of age.
- ⁱ A pregnancy test will be obtained for female participants of childbearing potential. Serum β -hCG will be performed at Screening (Visit 1), while urine pregnancy test will be performed at Visits 2 and 4 to 7 during study intervention. To continue in this study, a negative serum test must be documented at the Screening Visit (Visit 1) and negative urine tests must be documented at Day 1 Visit (Visit 2) to start study intervention and at Visits 4 to 6 to continue study intervention.

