Study Day	-14 to -1	1	Day 15 (± 3)^a (Phone Visit)	Day 29 (± 3)	Day 57 (± 3)	Day 113 (± 3)	Day 169 (± 3)	225 (±3)	281 (±3)	365 (+3)^b
Study Procedure										
Study intervention administration in the clinic ^j		X								
AE evaluation ^k	X	X	X	X	X	X	X	X	X	X
Study intervention dispensed ^l		X		X	X	X	X	X	X	
Study intervention compliance and accountability				X	X	X	X	X	X	X

^a Week 2 visit (Visit 3) will be a phone visit for all participants.

^b All enrolled participants who prematurely discontinue from the study, regardless of cause, are required to return for the EOT study assessments.

^c Physical examinations performed by medically qualified site personnel at Visits 1 and 10 may be repeated at the investigator's discretion.

^d Fecal impaction is defined as a hard mass in the lower abdomen identified on physical examination or a dilated rectum filled with a large amount of stool on rectal examination. If fecal impaction is documented during an optional repeat physical examination, the sponsor must be notified. If a rectal examination is performed, the medically qualified site personnel should assess for and document the presence of anal wink and normal anal tone.

^e A fecal impaction assessment is performed at the study Day 1 Visit (Visit 2) prior to study intervention administration. If the participant is impacted at Visit 2, the participant would not be eligible for the study.

^f Vital signs include weight, temperature (oral, rectal, or tympanic), and respiratory rate. Postural vital signs (supine and standing) include pulse rate and systolic and diastolic blood pressure. At all visits, postural vital signs must be obtained after participants have been in a supine position for at least 2 to 3 minutes, followed by a standing position for at least 1 minute.

^g Clinical laboratory tests consist of clinical chemistry, hematology, and urinalysis. All laboratory tests requiring blood draws should be collected at the same time.

^h The urine drug screen will be obtained at Screening (Visit 1) for all participants 12 to 17 years of age and, only if deemed necessary by the investigator, for participants 7 to 11 years of age.

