Linaclotide is a 14-amino acid peptide that acts on the apical surface of epithelial cells surrounding the intestinal lumen to stimulate the guanylate cyclase subtype C (GC-C) receptor. Linaclotide is approved for the treatment of irritable bowel syndrome with constipation (IBS-C) and chronic idiopathic constipation (CIC) in the United States, Canada, Japan, Australia, New Zealand, Kingdom of Saudi Arabia, and Mexico; for the treatment of IBS-C in China, the European Union (EU), Hong Kong, Macau, and Switzerland; and is being studied in other regions. By activating GC-C, orally administered linaclotide has been found to increase intestinal fluid secretion and intestinal transit, and to decrease visceral (abdominal) pain. Linaclotide has minimal oral bioavailability ($\leq 0.2\%$) in several animal species (Bryant 2010; Eutamene 2010) and is minimally absorbed with low systemic availability in adults. Refer to the Investigator's Brochure (IB) for a more detailed description of the chemistry, pharmacology, efficacy, and safety of linaclotide, based on studies conducted in animals, healthy volunteers, and in participants with IBS-C and CIC (linaclotide IB).

Two Phase 2 dose-ranging studies have been conducted with linaclotide in pediatric participants; one in FC, 6 to 17 years of age (LIN-MD-62), and one in IBS-C, 7 to 17 years of age (LIN-MD-63). Results from these two studies are summarized in Section 2.2.2.

This study will assess the long-term safety of linaclotide administered to pediatric participants with FC (total exposure with linaclotide for 24 weeks) or IBS-C (total exposure with linaclotide for 52 weeks) who have completed Study LIN-MD-62, LIN-MD-63, or LIN-MD-64:

- LIN-MD-62 (Phase 2): A Multicenter, Randomized, Double-blind, Placebo-controlled, Parallel-group, Safety and Efficacy Study of a Range of Linaclotide Doses Administered Orally to Children, Ages 6 to 17 Years, Who Fulfill Modified Rome III Criteria for Child/Adolescent FC
- LIN-MD-63 (Phase 2): A Multicenter, Randomized, Double-blind, Placebo-controlled, Parallel-group, Safety and Efficacy Study of a Linaclotide Dose Administered Orally to Children, Ages 7 to 17 Years, With Irritable Bowel Syndrome With Constipation (IBS-C) (ie, Fulfill Rome III Criteria for Child/Adolescent IBS and Fulfill Modified Rome III Criteria for Child/Adolescent Functional Constipation)

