- LIN-MD-64 (Phase 3): A Phase 3, Multicenter, Randomized, Double-blind, Parallel-group, Safety and Efficacy Study of Linaclotide in Pediatric Participants, Ages 6 to 17 Years, With Irritable Bowel Syndrome with Constipation (IBS-C) and of Linaclotide versus Placebo in Pediatric Participants with Functional Constipation (FC)

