4.3. Justification for Doses

The linaclotide dosages chosen for FC participants in this long-term safety study (72 and 145 µg) were well tolerated among participants 6 to 17 years of age with FC in LIN-MD-62. The safety profile was consistent with prior adult linaclotide studies for CIC. FC participants 6 to 17 years of

age who complete either LIN-MD-62 or LIN-MD-64, will have the option to enroll into this study. FC participants, 6 to 11 years of age, will receive open-label 72 µg linaclotide. FC participants, 12 to 17 years of age, will be randomly assigned open-label linaclotide at a 1:1 ratio to 72 µg linaclotide or 145 µg linaclotide.

The linaclotide doses of 290 µg or 145 µg once daily chosen for IBS-C participants in this long-term safety study were well tolerated among participants 12 to 17 years of age (290 µg dose) and 6 to 17 years of age (145 µg dose) with IBS-C in LIN-MD-63. The safety profile was consistent with prior adult linaclotide studies for IBS-C. While the 290 µg linaclotide dose is the highest dose being evaluated in IBS-C participants 6 to 17 years of age in the lead-in Phase 3 study LIN-MD-64, LIN-MD-63 completers who received ≤ 145 µg linaclotide or placebo in LIN-MD-63 will have the option to receive open-label linaclotide 145 µg once daily for 52 weeks. LIN-MD-64 completers with IBS-C will have the option to either remain on the same blinded linaclotide dose they were receiving in lead-in study LIN-MD-64 (blinded linaclotide 290 µg or 145 µg once daily) or to receive open-label linaclotide 290 µg once daily.

Dose modifications permitted for FC and IBS-C participants are described in Section [6.6](#).

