5.1.1. General Inclusion Criteria (All Participants)

- 1.01 Participant weighs ≥ 18 kg at the time the parent/guardian/LAR and/or caregiver has provided signed consent.
- 1.02 Female participants who have had their first menstrual period and are sexually active must agree to use a reliable form of contraception. Reliable contraception is defined in [Appendix 7](#).
- 1.03 Male or female participants must be 6 to 17 years of age (inclusive), at the time the parent/guardian/LAR and/or caregiver provides written informed consent and the participant must provide assent before the initiation of any study-specific procedures.
- 1.04 Participants must have completed study intervention in their lead-in study as defined in Section [4.1](#).
- 1.05 Female participants of childbearing potential must have a negative pregnancy test at both Screening (Visit 1) and at Study Day 1 (Visit 2) (Section [1.4](#) [SoA] and Section [10.7](#)).

5.1.2. Inclusion Criteria for Phase 3 LIN-MD-64 Completers and Phase 2 LIN-MD-63 Completers Who Enroll in LIN-MD-66 Within ≤ 28 Days From Last Study Intervention

- 2.01 Participants who turn 18 years of age prior to enrollment must provide consent for the study.

5.1.3. Inclusion Criteria for Phase 2 LIN-MD-62 or Phase 2 LIN-MD-63 and Phase 3 LIN-MD-64 Completers Who Enroll in LIN-MD-66 After > 28 Days From Last Study Intervention

- 3.01 Female participants of childbearing potential must have a negative serum pregnancy test at the Screening Visit (Visit 1) and negative urine pregnancy test prior to the first dose on the Day 1 Visit (Visit 2).

3.02 This criterion has been removed.

3.03 This criterion has been removed.

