9.0 Safety Analyses

9.1 General Considerations

All safety analyses or summaries will be performed by study intervention group using the safety population, for overall and for each age group (6 to 11 years and 12 to 18 years in FC; 7 to 11 years and 12 to 18 years in IBS-C) separately for FC and IBS-C participants.

For each safety parameter (laboratory, vital signs, body weight, height, and ECG), the baseline will be defined as below:

- If participants enroll into LIN-MD-66 within 28 days of last dose date of the lead-in study, baseline of the lead-in study will be used as the baseline value in LIN-MD-66.
- If participants enroll into LIN-MD-66 after 28 days of last dose date of the lead-in study, the last non-missing assessment made before the first dose of the study intervention in this study will be used as the baseline value in LIN-MD-66.

Safety data analyses will be provided descriptively based on the observed safety data, without data imputation for missing safety parameters.

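### The SAP's IBS-C age groups start at 7 years while the eligibility text admits age 6, so any 6-year-old with IBS-C would fall in no age group

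*SAP*

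**What the plan says.** SAP Section 9.1 requires all safety summaries overall and by age group, separately for FC and IBS-C, with these groups: "6 to 11 years and 12 to 18 years in FC; 7 to 11 years and 12 to 18 years in IBS-C". The same split is stated in SAP Sections 5.0, 6.0 (twice), 7.0, 7.1, 7.2 and 7.3 and in Appendix A, which makes nine statements in all. The SAP gives no reason for starting IBS-C at 7 and no rule for a participant aged 6. Section 7.1 derives age from the date of informed consent.

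On eligibility, Protocol Section 5.1.1, criterion 1.03, applies to all participants: "Male or female participants must be 6 to 17 years of age (inclusive", judged at consent. The design text in Protocol Sections 1.1 and 4.1 and in SAP Section 2.2 says that the study will "enroll pediatric participants (6-17 years of age) with FC or IBS-C". Protocol Appendix 6 gives a planned minimum age of 6 years for the study as a whole.

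For the IBS-C population of LIN-MD-64, the study title in Protocol Section 2 reads "Ages 6 to 17 Years, With Irritable Bowel Syndrome with Constipation (IBS-C", and Protocol Section 4.3 calls 290 µg the "highest dose being evaluated in IBS-C participants 6 to 17 years of age in the lead-in Phase 3 study LIN-MD-64".

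**The concern.** The age groups in an analysis plan should cover every age that the eligibility criteria allow. The FC groups do so and the IBS-C groups do not. As written, a 6-year-old with IBS-C who meets the criteria belongs to neither IBS-C age group.

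Safety is the study's primary objective, and the by-age tables are where a reader looks for an age pattern in adverse events, laboratory values, vital signs and ECGs. Any participants left out of those tables would be the youngest with IBS-C. The protocol itself treats young age as relevant to safety: Section 2.2.3.1 reports that tolerability in juvenile mice rises with age. The two age-group columns would also fail to sum to the overall column, with no explanation in the plan.

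**Working it through.** No sample size, power or error-rate figure bears on this point. The check compares sets of whole years and then asks whether a route exists for the uncovered age.

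**Step 1: ages allowed at consent.** Criterion 1.03 gives 6 to 17. Protocol Section 4.1 and criterion 2.01 add age 18 for those who enroll within 28 days of the last lead-in dose. The allowed set is {6, ..., 18}. No inclusion or exclusion criterion in Sections 5.1 and 5.2 sets a higher minimum for IBS-C.

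**Step 2: ages covered by the SAP.** Age in the SAP is taken at consent, the same time point as in criterion 1.03, so the two sets can be compared directly.

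| Indication | Allowed | SAP groups | Left over |
|---|---|---|---|
| FC | 6 to 18 | 6 to 11, 12 to 18 | none |
| IBS-C | 6 to 18 | 7 to 11, 12 to 18 | 6 |

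**Step 3: is there a route for a 6-year-old with IBS-C?** Criterion 1.04 requires completion of a lead-in study. For IBS-C that means LIN-MD-63 or LIN-MD-64.

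- LIN-MD-63 cannot supply one. Protocol Section 2 describes it as "one in IBS-C, 7 to 17 years of age (LIN-MD-63", Section 2.2.2 repeats that range, and the youngest group in Table 2-2 is 7 to 11.
- LIN-MD-64 could. Protocol Sections 2 and 4.3 both attach 6 to 17 to its IBS-C participants. Its treatment period is 12 weeks, well under a year, so a child treated soon after the sixth birthday could still be 6 at consent for LIN-MD-66.

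**Step 4: passages on the IBS-C minimum age, side by side.**

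| Place | Lower age | Scope |
|---|---|---|
| Criterion 1.03; Protocol 1.1 and 4.1; SAP 2.2; Appendix 6 | 6 | FC and IBS-C together |
| Protocol 2, LIN-MD-64 title | 6 | title of a two-indication study, attached to IBS-C |
| Protocol 4.3, on LIN-MD-64 | 6 | IBS-C |
| Protocol 10.10.1, urine drug screen | 6 | completers of all three lead-in studies enrolling after more than 28 days |
| Table 1-4 footnote h, urine drug screen | 7 | IBS-C completers of LIN-MD-63 and LIN-MD-64 enrolling after more than 28 days |
| All nine SAP age-group statements | 7 | IBS-C |

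The drug-screen rule is thus stated with two different lower ages for the same IBS-C participants: Section 10.10.1 uses 6, and Table 1-4 has "only if deemed necessary by the investigator, for participants 7 to 11 years of age".

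**Step 5: what a 6-year-old would and would not be counted in.** Such a participant is in the Safety Population (SAP Section 4.0), in the overall columns and in the listings. The age bands for potentially clinically significant values in SAP Appendix B start at 6 and do not differ by indication, so abnormal values would still be flagged. What is lost is the by-age columns.

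**The case against.** The strongest reply is that 7 is the intended IBS-C minimum and the SAP is right. All nine SAP statements give FC and IBS-C different lower limits side by side, which does not look like a slip. The protocol makes the same split in the drug-screen footnotes: for FC (Table 1-2) it is "only if deemed necessary by the investigator, for participants 6 to 11 years of age", while the IBS-C footnote starts at 7 and covers LIN-MD-64 completers too. The general statements of 6 to 17 pool the two indications and would be correct as a pooled range even with an IBS-C minimum of 7. The LIN-MD-64 title gives a single range for a study of both indications. Protocol Section 4.3 is a weak witness on this very point, because the same paragraph gives LIN-MD-63 as 6 to 17 for the 145 µg dose, against 7 to 17 elsewhere.

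Most of this stands. It shows that the gap may be empty in practice. It does not show that the documents agree. The footnote governs a urine drug screen rather than eligibility and conflicts with Section 10.10.1. If 7 is the minimum for IBS-C, no eligibility criterion says so. On either reading, some text needs correcting.

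A reader might go further and infer that 6-year-olds with IBS-C did enroll and were dropped from the safety analysis. The documents support neither part. Entry depends on LIN-MD-64 criteria that are not available here, and such participants would remain in the overall summaries and listings. A reader might also want a percentage of the lower age group. That would need the age distribution of LIN-MD-64 IBS-C completers, which the documents do not give, so no percentage is offered.

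**Conclusion.** The mismatch is established on the text: age 6 is the only allowed age outside both IBS-C groups, and the FC groups have no such gap. The consequence is conditional. If any LIN-MD-64 IBS-C completer is aged 6 at consent, the by-age safety tables omit that participant and do not sum to overall. The number affected is unknown and may be zero.

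This is a minor point. The study has no hypothesis and no inferential testing (SAP Sections 2.1 and 11.0), so only descriptive age-group tables are touched. The conclusion assumes that the table specifications, which SAP Section 1.0 places in a separate document, follow the SAP's groups. Different handling there cannot be excluded.

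**What to change.** Define the lower IBS-C age group as 6 to 11 years in SAP Sections 5.0, 6.0, 7.0 to 7.3 and 9.1 and in Appendix A. This covers every age that the eligibility text allows and changes no count if no 6-year-old with IBS-C enrolled. The cost is wording in nine places and one line in the age-group definition used for programming. No new data are needed.

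If the sponsor instead confirms 7 as the IBS-C minimum, keep the SAP groups and state that minimum in the protocol and in SAP Section 2.2. This costs more, because it touches criterion 1.03, which is an eligibility criterion, and so needs a protocol amendment.

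Either way, state the IBS-C minimum age once and reconcile it across Protocol Sections 1.1, 2 (the description of LIN-MD-64), 4.1, 4.3, 5.1.1 (criterion 1.03) and 10.10.1, Table 1-4 footnote h, Appendix 6, and SAP Section 2.2.

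Separately, the LIN-MD-63 age range in Protocol Section 4.3 should be reconciled with Sections 2 and 2.2.2. That is a wording correction and does not affect the age groups.

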9.2 Adverse Events

Adverse events (AEs) will be summarized and presented using primary MedDRA System Organ Classes (SOCs) and preferred terms (PTs) according to the version of the MedDRA coding dictionary used for the study at the time of database lock. The actual version of the MedDRA coding dictionary used will be noted in the AE tables and in the clinical study report.

9.2.1 Treatment-Emergent Adverse Events

An AE will be considered a treatment emergent adverse event (TEAE) if:

- The AE began on or after the date of the first dose of study intervention in LIN-MD-66; or
- The AE was present before the date of the first dose of study intervention in LIN-MD-66 but increased in severity or became serious on or after the date of the first dose of study intervention in LIN-MD-66.

However, an AE that occurs more than 30 days after the last dose of study intervention in LIN-MD-66 will not be counted as a TEAE.

An AE will be considered a treatment emergent serious adverse event (TESAE) if it is a TEAE that additionally meets any serious adverse event (SAE) criterion.

